3.2.2 ACT Training Content

3.2.2.1 In-person ACT sessions

The in-person ACT sessions will consist of structured techniques focused on helping participants cope with their pain more effectively. The sessions will follow a manual that was adapted from our previous pilot study for groups of patients with NF-related pain; the format for the current study has been adapted for use with individuals. Content also was based on previous manualized ACT interventions outlined in books (Dahl, Wilson, Luciano, & Hayes, 2005; Hayes et al., 1999) and articles (Masuda et al., 2011; Wicksell, Dahl, Magnusson, & Olsson, 2005; Wicksell et al., 2007) and used in prior ACT studies with chronic pain patients.

The ACT manual is presented in [Appendix U](#). In general, the content of the in-person and video chat sessions will be based on the six core therapeutic processes of ACT, each of which are interrelated and build upon the others:

(1) Mindfulness. Mindfulness is of central importance in ACT. Participants will be taught to practice mindfulness exercises to help them be aware of internal and external events as they occur. Engaging in mindfulness helps people become more aware of their automatic, maladaptive thoughts and be more flexible in their reactions to them. Basic mindfulness exercises, such as focusing on one's breathing or on particular sights or sounds, will help individuals learn to observe and describe these things in a neutral manner. Then the focus of mindfulness exercises will be extended to thoughts about the person's pain.

(2) Acceptance. Patients will be encouraged to be willing to experience their pain and the thoughts and feelings they have about their pain without judging or trying to change them. They will be taught to let go of their struggle against pain as a means of opening themselves up to more adaptive ways of living. One's willingness to experience pain can lead to the creation of a more full and vital life, since all the energy once spent avoiding pain can now be focused on valued activities and goals.

(3) Cognitive Defusion. Defusion refers to the process of separating the words people use from their literal meaning. For example, just because a patient has the thought "I can't stand this pain" does not make it true. Participants will be taught to observe their thoughts without necessarily believing them to be true or acting upon them. The therapist accomplishes this by labeling the person's thoughts as only thoughts rather than known facts. If a patient states "I can't go to the football game because my arm hurts" the therapist can reframe that as "You're having the thought that you can't go to the game" to emphasize that the statement may not be true. This gradually helps the people disentangle themselves from their thoughts, and frees them up to make choices based on factors other than the immediate thoughts they have about their pain.

(4) Self as Context. This aspect of ACT refers to helping participants become more aware of a sense of self from which they can observe and accept their thoughts, emotions, and experiences. Doing so helps individuals become disentangled from their maladaptive thoughts, since they are encouraged to experience them as an observer rather than a participant. This, in turn, helps the participant to view his or her struggle with more objectivity and compassion.

(5) Defining Valued Directions. Patients will participate in exercises aimed at helping them define their core values and then will examine the ways in which their current behaviors are interfering with their ability to live their life consistent with their values. The therapists will demonstrate how focusing on avoidance of pain means that one is not focusing on valued activities. Living in accordance with one's values and without pain may not be possible. This is an important point for patients to realize.

(6) Committed Action. Participants will be asked to define concrete goals that are consistent with their core values, and then commit to living in accordance with these goals. Potential barriers to reaching their goals will be addressed, with specific focus on how to respond when faced with obstacles. Therapists also will focus on how to engage the support of significant others (for example, parents, friends, spouses) in one's pursuit of his or her goals.

Participants will complete practice exercises on their own in between the two sessions. At the end of the second session, patients will be given a workbook to take home that includes a summary of the topics discussed during the sessions and exercises for continuing to work on ACT techniques at home. In addition, patients will be given an audio CD or MP3 download that contains mindfulness meditations geared towards individuals with chronic pain ("Mindfulness Meditation for Pain Relief" by Jon Kabat-Zinn).

3.2.2.2 Emails

Weekly emails will be sent to each ACT group participant during weeks 1 – 8 (see [Appendix Q](#)). These emails will contain a brief summary of a topic relevant to ACT concepts, and an exercise or assignment for the participant to complete that week. If the participant emails the trainer with a specific question, the trainer will respond as soon as possible (typically within 24 hours, not including weekends). Any medical questions will be referred to the patient's medical provider. The main content of the emails will be the same across patients, but certain examples in the emails may be adapted slightly depending on the patient's age or individual goals. For example, we may discuss a 16-year old patient's goal of doing well in school, or a 28-year old patient's goal of joining a book club.

3.2.2.3 Video chat Sessions

Each individual, 30-minute video chat session will be structured as follows (approximately): 5 minutes to review the topics from the weekly emails, 15 minutes to introduce a new topic (related to previous content), and 10 minutes to discuss any difficulties the patient may be experiencing in relation to their pain or the intervention exercises. The manual for video chat sessions is in [Appendix S](#).

3.3 QUESTIONNAIRES

3.3.1 Patient Questionnaires

3.3.1.1 Pain Interference

The Pain Interference Index (PII) is a 6-item questionnaire meant to assess the degree to which pain has interfered with daily activities in the past week ([Appendix C](#)). This measure initially was developed and validated in Sweden with youth with longstanding idiopathic pain (Wicksell, Melin, Lekander, & Olsson, 2009b). In collaboration with the Swedish researchers, the authors of the current study translated the measure to English and also created a parallel parent report version (PII-P) and an adult self-report version. The youth self-report PII has been validated in patients ages 6 to 25 years with NF1 and other chronic illnesses (Martin et al., 2014). For this study, this version will be administered to patients ages 16 to 17 and to 18-25 year olds who are still in school. The adult self-report version is parallel to the youth self-report version, with minor wording modifications made (changing “school” to “work”). Initial reliability and validity data of the adult self-report version are positive ($\alpha = .94$; manuscript in preparation). Both versions of the scale take about 2 minutes to complete.

The PROMIS Pain Interference scales will be administered as another assessment of pain interference (Appendices C and D); (Amtmann et al., 2010; Varni et al., 2014). The adult 8-item short form will be administered to participants ages 18 - 59, and the pediatric 8-item short-form will be given to participants ages 16 and 17 years. Both of these scales ask the respondent to consider how much pain has interfered with things like sleep, mood, and leisure activities, in the past week. Items are formatted on 0-4 Likert scales. These measures each take about 2 minutes to complete. The PII and the PROMIS pain interference scales are both being given since they each have advantages and disadvantages. Specifically, the PII’s limited items may not capture all relevant aspects of pain interference in NF1, but this measure has strong preliminary reliability and validity data in this population, which the PROMIS does not yet have. Moreover, giving both measures in conjunction is the current recommendation of the Patient-Reported Outcomes (PRO) working group of the Response Evaluation in Neurofibromatosis and Schwannomatosis (REiNS) collaboration.

3.3.1.2 Disease-specific Quality of Life

The PedsQL NF Module, Adult form is a questionnaire designed to assess various aspects of quality of life in individuals with NF1 (Nutakki, Hingtgen, Monahan, Varni, & Swigonski, 2013) ([Appendix F](#)). Items on this scale ask the respondent to indicate the extent to which they have had problems performing various activities over the past month, using a 0 – 4 Likert scale (0 = Never, 4 = Almost Always). The subscales that will be administered on this study include Physical Functioning (7 items) and Daily Activities (12 items). Mean scores for each subscale are linearly transformed to a 0-100 scale, and then can be compared to means and standard deviations of a normative group of patients with NF1. These two subscales should take less than five minutes to complete.

3.3.1.3 Pain-related Anxiety

The Pain Anxiety Assessment Scale – 20 (PASS-20) is a 20-item measure developed to assess pain-related anxiety in medical patients (McCracken & Dhingra, 2002; see [Appendix G](#)). Items are answered on a 6-point Likert scale with anchors of “never” and “always.” Responses provide

a total score and scores on four subscales: Cognitive Anxiety, Pain-related Fear, Escape and Avoidance, and Physiological Anxiety. The PASS-20 is reliable (Cronbach's alpha = .81) and valid (L. M. McCracken & Dhingra, 2002; Roelofs et al., 2004). The measure takes about 5 minutes to complete.

3.3.1.4 Depression

The Center for Epidemiological Studies – Depression scale (CES-D) (Radloff, 1977) is a 20-item measure originally developed for use with individuals 18 years and older, and has since been validated with adolescents as young as 12 years (Garrison, Addy, Jackson, McKeown, & Waller, 1991). Respondents are asked to rate how frequently in the past week they have experienced a list of symptoms, such as feeling depressed, enjoying life, having problems sleeping, and feeling liked by people. Items are scored on a 0 (rare or none of the time) to 3 (most of all of the time) format. Individual responses yield scores on four subscales: depressive affect, positive affect, somatic activity, and interpersonal. A total depression score is obtained that can range from 0 to 60, with higher scores representing worse depressive symptoms. This tool has been shown to be valid and reliable in clinical populations (Orme, Reis, & Herz, 1986) and with medical patients, including those with chronic pain (Hann, Winter, & Jacobsen, 1999; Turk & Okifuji, 1994). This questionnaire takes approximately 5 minutes to complete (See [Appendix H](#)).

3.3.1.5 Pain Intensity

The Numeric Rating Scale – 11 (NRS-11) consists of two questions that assess pain intensity. The items are formatted along a horizontal line with from 0 (no pain) to 10 (worst pain imaginable) spaced equidistant along the line ([Appendix I](#)). Respondents circle the one number that best represents their pain currently, and in the past week. This measure is widely used and is recommended for use in clinical trials for patients with chronic pain, including NF1 (Wolters et al 2013; Gilron & Jensen, 2011). It takes less than one minute to complete.

3.3.1.6 Coping with Pain

The Chronic Pain Acceptance Questionnaire (CPAQ; (L. M. McCracken et al., 2004) was designed to assess one's ability to accept his or her pain, and is typically used with patients ages 18 years and older. Respondents answer 20 questions on a 0 (never true) to 6 (always true) rating scale, with higher scores indicating higher levels of acceptance. Scores are obtained on two subscales (Activities Engagement and Pain Willingness) and an Acceptance Total scale. Reliability and validity, and sensitivity to change have been demonstrated (Huggins et al., 2012; Vowles & McCracken, 2008). The CPAQ takes approximately 5 minutes to complete (See [Appendix J](#)).

3.3.1.7 Psychological Inflexibility

The Psychological Inflexibility in Pain Scale (PIPS) is a 12-item measure that assesses the extent to which an individual engages in avoidance of activities because of their pain (experiential avoidance) and inflexible thinking about their pain (cognitive fusion) (Wicksell, Lekander, Sorjonen, & Olsson, 2010); [Appendix K](#)). The measure asks respondents to rate how true the statements are for them currently, on a Likert scale of 1 (never true) to 7 (always true). Eight of the items are summed to yield a score on the Avoidance subscale, and four of the items are summed for the Fusion subscale. A total score also is obtained by summing all 12 items. The PIPS has been found to have good internal consistency and strong correlations with criterion

variables such as pain intensity, use of pain medication, and other measures of activity avoidance (Trompeter et al., 2014; Wicksell et al., 2010). The form takes about 3 minutes to complete.

3.3.1.8 Recent Life Events

Because stressful life events may impact pain and coping, we will administer the Life Events Scale (LES), a measure designed to assess significant events that have occurred in the patient's life in the past six months ([Appendix L](#)). The patient is asked to indicate which events have occurred in their life from a list of 43 potential events. This scale has shown reliability and validity (Elliott-Desorbo, Martin, & Wolters, 2009).

3.3.1.9 Pain Management

The Pain Management Inventory (PMI) was developed by our group to assess what techniques patients use to manage their pain, including pharmacological and non-pharmacological treatments. Specifically, respondents are asked what pain medications they have taken in the past month and how frequently. Another question asks about any other (non-pharmacological) techniques in which participants have engaged (e.g., relaxation, massage) for coping with pain in the past month. At the 6-month time point, there is an additional question on this form that asks whether the patient has had surgery for their NF1 in the past six months. This measure takes about 2 minutes to complete (see [Appendix M](#) and [Appendix N](#)).

3.3.1.10 Adherence to ACT Intervention

The ACT Inventory was developed by our group to assess the frequency with which participants have engaged in ACT strategies in the past month. Six items ask how much participants have used mindfulness, defusion, and other ACT techniques taught during the intervention to help them cope with pain in their daily lives. One item asks how much the person liked participating in the study. This will be given at follow-up time points only, and takes about 2 minutes to complete ([see Appendix O](#)).

3.3.1.11 Subjective Change Rating

The Patient Global Impression of Change (PGIC) scale is one item used to assess the patient's overall impression of their level of pain interference at the end of the study compared to baseline (see [Appendix P](#)). Versions of this scale have been used in studies of various pain populations (Arnold, Zlateva, Sadosky, Emir, & Whalen, 2011; Mohammad et al., 2014). Also, this measure has been recommended by the Initiative on Methods, Measurement, and Pain Assessment in Clinical Trials (IMMPACT) for use in clinical trials involving chronic pain (Dworkin et al., 2005). It takes less than one minute to complete.

3.3.2 ECG procedures

An ECG will be given to assess heart rate variability. In accordance with recommendations from the European Society of Cardiology and North American Society of Pacing and Electrophysiology Task Force ("Heart rate variability. Standards of measurement, physiological interpretation, and clinical use. Task Force of the European Society of Cardiology and the North American Society of Pacing and Electrophysiology," 1996), the reading will occur for 5 minutes while the patient is lying down (for ease of electrode placement). We will obtain several measurements, including the standard deviation of the average NN (normal-to-normal) interval (SDANN) and the square root of the mean squared differences of successive NN intervals

(RMSSD). At baseline and follow-up visits, we will attempt to take measurements at approximately the same time of the day, since HRV can fluctuate throughout the day. Since the Wait-List group will essentially have two baseline assessments (one at enrollment and one before they start the ACT intervention), patients in this group will have three ECGs while the Immediate Intervention group will get a total of two ECGs. A standard “ECG Procedures” form will be used to capture any abnormalities in administration, such as if a patient coughs or talks during the administration. This form also will record whether the patient had any caffeine that day, and approximately how much, since caffeine can impact heart rate.

3.3.3 Word Reading test

The Word Reading subtest from the Wide Range Achievement Test 4 will be administered to patients in order to estimate their reading ability. This task is also a widely recognized proxy of cognitive functioning. This will allow us to control for this variable statistically, if there are any systematic differences related to how people with different reading skills (and proximal cognitive abilities) respond to the intervention, which is conceptually diverse and involves reading weekly emails. For this task, patients are asked to read a list of words aloud to the examiner. The Word Reading subtest takes about one to two minutes to complete.

Abbreviated Title: ACT Therapy for NF1 Related Pain

Version Date: 02/19/2019

3.4 STUDY CALENDAR

| Procedure | Screening | Baseline | Week 8 | Week 16 | Week 32 | Week 40 |
|---------------------------|-----------|----------|--------|---------|---------|---------|
| History and Physical Exam | X | | | | | |
| Pain Interference Index | X | | | | | |
| Questionnaires* | | | | | | |
| • ACT | | X | X | | X | |
| • WL | | X | X | X | | X |
| Word Reading | | | | | | |
| • ACT | | X | | | | |
| • WL | | X | | | | |
| Electrocardiogram | | | | | | |
| • ACT | | X | X | | | |
| • WL | | X | X | X | | |
| Intervention | | | | | | |
| • ACT | | X | | | | |
| • WL | | | X | | | |
| Adverse Events | | X | X | X | X | X |

*as listed in Section 3.3.1.

3.5 COMPENSATION

To thank participants for their time during participation, participants will receive \$30 for each visit. Funds will be distributed in accordance with the Clinical Center's Research Volunteer system, such that participants can have the money directly deposited to a bank account or have a check mailed to them.

3.6 CRITERIA FOR REMOVAL FROM PROTOCOL

Participants will be removed from this study for any of the following:

- Screen failure
- Completion of protocol requirements
- Participant requests to be withdrawn from study
- Patient begins a new treatment that is likely to impact pain (e.g., MEK inhibitor)
- Patient reports a significant increase in pain that necessitates a new pain treatment or a medical procedure (i.e., surgery) that would notably impact pain levels. (These patients could re-enroll at a later date, if they again met criteria for this study and had not received the full in-person ACT intervention).
- Lost to follow up
- Investigator feels that it is in the best interest of the participant to withdraw from participation.

Note: all minors, who have signed the standard consent or assent, will be kept on study and followed until the age of 18 to allow consent.

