2 ELIGIBILITY ASSESSMENT AND ENROLLMENT

2.1 ELIGIBILITY CRITERIA

2.1.1 Inclusion Criteria for Participant

2.1.1.1 Patients must be between 16 and 59 years of age at the time of the baseline assessment. Because the research on the effectiveness of ACT with younger children is still emerging, children 15 and younger will be excluded from the present study.

2.1.1.2 Diagnosis of NF1 through germline mutation OR clinical diagnosis; for the clinical diagnosis of NF1 all study subjects must have two or more diagnostic criteria for NF1 listed below (NIH Consensus Conference):

1. Six or more café-au-lait spots (≥ 0.5 cm in prepubertal subjects or ≥ 1.5 cm in postpubertal subjects)
2. ≥ 2 neurofibromas or 1 plexiform neurofibroma
3. Freckling in the axilla or groin
4. Optic glioma
5. Two or more Lisch nodules
6. A distinctive bony lesion (dysplasia of the sphenoid bone or dysplasia or thinning of long bone cortex)
7. A first-degree relative with NF1

2.1.1.3 Participants must have documentation of a PN, based on either clinical exam or imaging.

2.1.1.4 Patient must self-report having chronic pain for at least the past 3 months that has interfered with their daily functioning, as assessed by the Pain Interference Index (must get a mean score of 2.0 or higher, or score a 3 on three or more individual items).

2.1.1.5 Patients must have regular access to a computer or tablet with internet access.

2.1.1.6 Ability of subject or Legally Authorized Representative (LAR) to understand and the willingness to sign a written informed consent document.

2.1.1.7 No anticipated major changes in their pain treatment regimen (i.e., new class of pain medication starting or change in the class of pain medication) or enrollment on a new treatment study presumed to impact pain in the near future.

2.1.1.8 Subjects must be able to read and comprehend the English language, since the highly trained ACT therapists are not fluent enough to conduct the trainings in Spanish or other languages.

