| 5. affected your ability to do physical activities (like run, walk up stairs, play sports, do chores)? | 0 | 1 | 2 | 3 | 4 | 5 | 6 |
| 6. affected your sleep? | 0 | 1 | 2 | 3 | 4 | 5 | 6 |

Three or more items answered as “some”? Yes No

OR

Mean score of 2.0 or above? Yes No

Okay, now just four more questions:

[Circle the patient’s responses to the following questions:]

| | | |
|--|-----|----|
| • How long have you had this pain? (≥ 3 months?) | Yes | No |
| • Do you have access to a computer, tablet, or smartphone with internet capability? | Yes | No |
| • Do you have any problems reading English? | Yes | No |
| • Are you planning to start any other new studies for treating your pain or your tumors? | Yes | No |

- If not eligible: I’m sorry, but you are not eligible for the study because _____. However, if you are interested, I can provide you with some online resources about ACT that you can read on your own.
- If eligible: Okay, these initial screening questions suggest that you are eligible for the study. Now I’ll tell you a little more about it to see if you are interested.

IV) Procedures

- People who participate in this study will come to the NIH two to three times. The first time, you would come for about two days. During this visit:
 - Randomization – we will randomly assign people to the immediate intervention group or to the delayed intervention group.
 - All patients will:
 - Fill out questionnaires asking about pain, quality of life, emotional well-being
 - Get an electrocardiogram, or EKG – painless, to read heart rate
 - Immediate Intervention group –

- This group will stay and do four hours of ACT Training (two 2-hour sessions) with a psychologist or psychology associate.
- Delayed/Wait-list group –
 - Go home and do nothing different for two months, return for intervention after 8 weeks. During this time, if you were to start a new pain treatment or treatment study that might impact your level of pain, we would have to remove you from this study.

V) ACT Training

- You will learn some techniques that have been found effective for helping people deal with pain; ACT does not get rid of pain, it helps people change their relationship with their pain. In other words, instead of trying to fight your pain, we can talk about ways of living with your pain while focusing your energy on things that are most important to you. In this way, we try to help you have the best quality of life you can have, even while you have pain.

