- You will continue to practice the ACT techniques at home:
 - Weekly emails – on an ACT-related topic with an assignment, something to practice during that week
 - Biweekly video chat sessions with a trainer to check on progress, continue to work on ACT techniques

VI) Follow-up

- All patients will return to the NIH after they complete the 8-week intervention:
 - Repeat questionnaires and EKG
- Final follow-up 6 months later from home
 - Repeat questionnaires from home computer
- To thank you for your time, we will be providing participants with a small amount of money each time they complete the follow-up questionnaires. We will also cover the costs of travel and some meals during your visits.

VII) Patient Interested?

Does this sound like something you would be interested in?

If no: Thank you for your time.

If yes: Okay, great! Let's try to find some possible dates when you could come for your first visit (ask about any upcoming surgeries that we may need to schedule around).

If eligible and interested, find possible dates for first visit:

Abbreviated Title: ACT Therapy for NF1Related Pain

Version Date: 02/19/2019

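### Section 3.6 takes randomised patients off study for pain-related events with no week-8 PII provided for, and 6.1 names no analysis set or missing-data method, so the primary contrast is open to selective loss

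*Combined protocol and SAP*

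**What the plan says.** Section 3.6 lists the grounds for removal from the study. Three bear on pain or on discretion:

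- "Patient begins a new treatment that is likely to impact pain", with a MEK inhibitor as the example.
- "Patient reports a significant increase in pain that necessitates a new pain treatment or a medical procedure"; the procedure (surgery is named) must be one that would notably affect pain levels.
- "Investigator feels that it is in the best interest of the participant to withdraw from participation".

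Patients removed for increased pain "could re-enroll at a later date, if they again met criteria for this study and had not received the full in-person ACT intervention". A closing note in 3.6 keeps minors who have signed on study until age 18 so that they can consent as adults.

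Section 3.6.1, the off-study procedure, is a status form to the registration office. The calendar in 3.4 has no off-study assessment. Section 3.1.2 brings both groups back at week 8, and no later than 12 weeks after the first visit, without mentioning patients already removed.

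Section 6.1 compares mean PII change from baseline to week 8 by a two-sided t-test at 0.05, with ANCOVA as an option for baseline imbalance. It names no analysis set, no method for missing week-8 scores and no sensitivity analysis. Section 6.2 provides for dropout by enrolling up to 90 where 82 are needed.

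**The concern.** The pain-related grounds can arise after randomisation, and a marked rise in pain lies close to the primary outcome. A change-score t-test needs a week-8 value, and the plan supplies none once a patient is off study. Patients removed for such reasons may have a different course from those who stay, so the retained groups need no longer be the groups that were randomised. Extra enrolment restores the number of patients but not the comparability of the arms.

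The re-enrolment rule adds a gap. By 3.1.1, ACT patients typically finish both in-person sessions by day 2, so in practice re-entry is open mainly to wait-list (WL) patients before their week-8 crossover. The plan does not say whether a returner is randomised again, keeps the first arm, or is counted once or twice.

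The note on minors is hard to square with removal for patients aged 16 and 17. It concerns consent and supplies no week-8 PII.

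**Working it through.** **The plan's own figure.** Inputs from 6.1: difference -0.68, SD of change 1.3 (ACT) and 0.8 (WL), two-sided alpha 0.05.

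- SE at 41 per arm = sqrt((1.3² + 0.8²)/41) = 0.238. Noncentral-t power is 80.5%, and 79.5% at 40 per arm. The stated 41 reproduces.
- Enrolment allowance: 90 - 2×41 = 8, and 8/90 = 8.9%. This covers dropout over all follow-up; it is not a rate of removal by week 8.

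**Effect of selective removal (illustration; the removal fractions are assumptions).** Take normal changes with the SDs of 6.1 and a true difference of -0.68. If the worst fraction f of an arm is removed, the mean of the rest moves by -SD×k, where k = φ(z)/(1-f) and z is the (1-f) normal quantile. If change correlates r with an unobserved (latent) normal score that decides removal, the movement is -r×SD×k.

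- k = 0.1950 at f = 10%; k = 0.0982 at f = 2/45.
- Both arms: -0.68 + r×k×(0.8 - 1.3).
- WL only: -0.68 + r×0.8×k.
- ACT only: -0.68 - r×1.3×k.

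| f | r | both arms | WL only | ACT only |
|---|---|---|---|---|
| 10% | 1 (upper bound) | -0.78 | -0.52 | -0.93 |
| 10% | 0.5 | -0.73 | -0.60 | -0.81 |
| 2/45 | 1 (upper bound) | -0.73 | -0.60 | -0.81 |
| 2/45 | 0.5 | -0.70 | -0.64 | -0.74 |

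Here r is the correlation with the latent score. The correlation with removal itself is r×φ(z)/sqrt(f(1-f)). For r = 0.5 that is 0.5×0.585 = 0.29 at 10% and 0.5×0.455 = 0.23 at 2/45. The shift with equal removal in both arms comes only from the unequal SDs; with equal SDs it is zero.

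**Recovery after removal.** Suppose 10% of the WL arm is removed and the full WL arm has mean change 0. If the removed patients also average 0 at week 8, there is no bias. If they average -1.0 (improved by then), the retained WL mean is 0.1×1.0/0.9 = +0.111, and the contrast becomes -0.68 - 0.111 = -0.79. That is the opposite direction from WL-only removal of the worst changers.

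**The case against.** Screening should keep such removals few. Section 2.1.1 requires "No anticipated major changes in their pain treatment regimen", 2.1.2.3 makes patients wait a year after starting a medical treatment that may affect pain, and the phone script asks "Are you planning to start any other new studies for treating your pain or your tumors" and tells staff to "ask about any upcoming surgeries that we may need to schedule around". The removal criteria are the same in both arms and narrowly worded: the pain increase must be significant and the procedure must notably affect pain. All of this stands. It limits the number of removals but cannot exclude unanticipated events over 8 to 12 weeks, which are what 3.6 is written for. Equal criteria do not guarantee equal removal in an unblinded trial with a self-reported trigger.

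Removing patients whose pain treatment changes also fits a question about a stable regimen. That is a legitimate choice of estimand, but 6.1 does not state it, and dropping such patients without further assumptions does not estimate it.

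Three stronger readings are tempting, and the documents do not support them.

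- A reader might infer that the plan prescribes a completers analysis. Section 6.1 is silent; that the contrast would rest on retained patients is an inference from the absence of week-8 scores.
- A reader might infer that the bias favours ACT or is large. No removal rate is given, and the illustrations run both ways.
- A reader might take the script's wait-list warning, "treatment study that might impact your level of pain, we would have to remove you from this study", as evidence of unequal removal. The script describes both groups to every interested candidate before randomisation, so future ACT patients hear it too.

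**Conclusion.** The concern holds in this form: the plan removes randomised patients for events related to pain, provides no week-8 PII for them, and defines neither the analysis set nor the handling of missing scores. The primary contrast is therefore open to selective loss. It should be fixed before analysis.

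The illustrated contrasts run from -0.52 to -0.93 around a true -0.68 in the extreme cases at 10% removal. With 2 of 45 removed and a latent correlation of 0.5, the shift is only 0.02 to 0.06. These figures rest on assumed removal fractions, normality and the SDs in 6.1. They show that bias is possible, not that it is material, and it may be zero or reversed if removed patients recover. The counting of re-enrolled patients and the conflict over minors are plain gaps that do not depend on any of these assumptions.

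**What to change.** Leave the clinical criteria for removal unchanged.

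- **Section 3.6:** separate stopping the intervention from stopping outcome collection. Seek the week-8 PII and questionnaires online from every randomised patient who has not withdrawn consent. Section 4.1 already has all questionnaires on computer or tablet, and 3.1.2 already accepts home completion for the wait-list third visit. Reconcile the note on minors with removal.
- **Section 6.1, analysis set:** analyse all randomised patients, each counted once in the arm first assigned. A returner is not a new unit.
- **Section 6.1, missing scores:** use multiple imputation with arm, age stratum and baseline PII, plus a tipping-point analysis.
- **New pain treatment up to week 8:** record its date by bringing forward an item like item 4 of Appendix N, which asks about new NF1 treatments with a date but only at six months. The medication history at screening and the Pain Management Inventory at baseline and week 8 allow new drugs to be detected by comparison, but give no start dates.
- **Sensitivity and reporting:** add a stable-regimen sensitivity analysis that sets values after such treatment to missing, and report removals by arm and reason.

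The cost is amendment wording, one dated item and a few online questionnaires. Section 7.5.2 indicates that some participants have already finished, so new collection may not reach everyone; the analysis and counting rules can still be fixed.

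The statistical price is some dilution. If 10% of each arm start a new treatment and the arms then do not differ among them (an assumption), the contrast is 0.9×(-0.68) = -0.61, with about 76% power at 45 per arm. If those patients are instead lost non-selectively, 45×0.9 = 40.5, so about 40 per arm remain with about 79.5% power. If the team prefers the stable-regimen question as primary, 6.1 should say so and state the assumptions.
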